Appendix 2: Decimal place

Category for Lab	Lab Test Short Name	Lab Test Name	Original Units	Standard Units	Conversion Factor	Decimal Place
CHEMISTRY	ALP	Alkaline Phosphatase	U/L	U/L	1	0
CHEMISTRY	ALT	Alanine Aminotransferase	U/L	U/L	1	0
CHEMISTRY	AST	Aspartate Aminotransferase	U/L	U/L	1	0
CHEMISTRY	CA	Calcium	mmol/L	mmol/L	1	2
CHEMISTRY	CL	Chloride	mmol/L	mmol/L	1	1
CHEMISTRY	CRP	C Reactive Protein	mg/L	mg/L	1	2
CHEMISTRY	GGT	Gamma Glutamyl Transferase	U/L	U/L	1	0
CHEMISTRY	GLUC	Glucose	mmol/L	mmol/L	1	2
CHEMISTRY	K	Potassium	mmol/L	mmol/L	1	2
CHEMISTRY	LDH	Lactate Dehydrogenase	U/L	U/L	1	0
CHEMISTRY	MG	Magnesium	mmol/L	mmol/L	1	2
CHEMISTRY	PHOS	Phosphate	mmol/L	mmol/L	1	2
CHEMISTRY	SODIUM	Sodium	mmol/L	mmol/L	1	0
HEMATOLOGY	BASO	Basophils	10 ⁹ /L	10 ⁹ /L	1	2
HEMATOLOGY	BASOLE	Basophils/Leukocytes	%	%	1	1
HEMATOLOGY	EOS	Eosinophils	10 ⁹ /L	10 ⁹ /L	1	2
HEMATOLOGY	EOSLE	Eosinophils/Leukocytes	%	%	1	1
HEMATOLOGY	HBDNA	Hepatitis B DNA	IU/mL	IU/mL	1	0
HEMATOLOGY	HBSAG	Hepatitis B Virus Surface Antigen	IU/mL	IU/mL	1	3
HEMATOLOGY	HCT	Hematocrit	%	%	1	1
HEMATOLOGY	HGB	Hemoglobin	g/L	g/dL	0.1	1
HEMATOLOGY	LYM	Lymphocytes	10 ⁹ /L	10 ⁹ /L	1	2
HEMATOLOGY	LYMLE	Lymphocytes/Leukocytes	%	%	1	1
HEMATOLOGY	MCH	Ery. Mean Corpuscular Hemoglobin	pg	pg	1	1
HEMATOLOGY	MCHC	Ery. Mean Corpuscular HGB Concentration	g/L	g/L	1	0
HEMATOLOGY	MCV	Ery. Mean Corpuscular Volume	fL	fL	1	1

Category for Lab	Lab Test Short Name	Lab Test Name	Original Units	Standard Units	Conversion Factor	Decimal Place
HEMATOLOGY	MONO	Monocytes	10 ⁹ /L	10 ⁹ /L	1	2
HEMATOLOGY	MONOLE	Monocytes/Leukocytes	%	%	1	1
HEMATOLOGY	NEUT	Neutrophils	10 ⁹ /L	10 ⁹ /L	1	2
HEMATOLOGY	NEUTLE	Neutrophils/Leukocytes	%	%	1	1
HEMATOLOGY	PLAT	Platelets	10 ⁹ /L	10 ⁹ /L	1	0
HEMATOLOGY	RBC	Erythrocytes	10 ¹² /L	10 ¹² /L	1	2
HEMATOLOGY	RETI	Reticulocytes	10 ⁹ /L	10 ⁹ /L	1	1
HEMATOLOGY	RETICH	Ret. Corpuscular Hemoglobin Content	pg	pg	1	1
HEMATOLOGY	WBC	Leukocytes	10 ⁹ /L	10 ⁹ /L	1	2
IRON INDICES	FERRITIN	Ferritin	ug/L	ng/mL	1	1
IRON INDICES	IBCU	Unsaturated Iron Binding Capacity	umol/L	umol/L	1	1
IRON INDICES	IRON	Iron	umol/L	umol/L	1	1
IRON INDICES	TFERRIN	Transferrin	g/L	g/L	1	2
IRON INDICES	TFRRNSAT	Transferrin Saturation	%	%	1	1
URINALYSIS	PH	pH				0
URINALYSIS	PHOS	Phosphate	mmol/L	mmol/L	1	2

Appendix 3: List of TFLs

Table 14.1.1 Subject Enrollment

Table 14.1.2 Number of Subjects Randomised by Site and Treatment Group

Table 14.1.3 Subject Disposition

Table 14.1.4 Subject Populations

Table 14.1.5.1 Demographic and Baseline Characteristics (SS)

Table 14.1.5.2 Demographic and Baseline Characteristics (FAS)

Table 14.1.6.1 Underlying Cause for IDA

Table 14.1.6.2 Medical History

Table 14.1.7.1 Medication History

Table 14.1.7.2 Concomitant Medication

Table 14.1.8.1 Study Drug Exposure

Table 14.1.8.2 Study Drug Compliance

Table 14.2.1.1 Analysis of Percentage of Subjects Achieving an Increase in Hb \geq 2g/dL (Responders)
- Baseline to any Time up to Week 8 (PPS)

Table 14.2.1.2 Analysis of Percentage of Subjects Achieving an Increase in Hb \geq 2g/dL (Responders)
- Baseline to any Time up to Week 8 (FAS)

Table 14.2.2.1 Summary of Subjects Achieving an Increase of Hb ≥ 2 g/dL from Baseline to Weeks 2, 4, 6, and 8 (PPS)

Table 14.2.2.3 Summary of Subjects Achieving an Increase in Hb ≥ 2 g/dL from Baseline at Weeks 2, 4, 6, and 8 (FAS)

Table 14.2.2.2 Analysis of Percentage of Subjects Achieving an Increase in Hb ≥ 2 g/dL from Baseline to Weeks 2, 4, 6, and 8 (PPS)

Table 14.2.2.4 Analysis of Percentage of Subjects Achieving an Increase in Hb ≥ 2 g/dL from Baseline at Weeks 2, 4, 6, and 8 (FAS)

Table 14.2.3.1 Summary of Haemoglobin (g/dL) Data (Absolute and Change from Baseline) Over Time (PPS)

Table 14.2.3.3 Summary of Haemoglobin (g/dL) Data (Absolute and Change from Baseline) Over Time (FAS)

Table 14.2.5.1 Summary of Transferrin Saturation (%) Data (Absolute and Change from Baseline) Over Time (PPS)

Table 14.2.5.3 Summary of Transferrin Saturation (%) Data (Absolute and Change from Baseline) Over Time (FAS)

Table 14.2.6.1 Summary of Serum Ferritin (ng/mL) Data (Absolute and Change from Baseline) Over Time (PPS)

Table 14.2.6.3 Summary of Serum Ferritin (ng/mL) Data (Absolute and Change from Baseline) Over Time (FAS)

Table 14.2.3.2 Analysis of Change in Haemoglobin (g/dL) Over Time (Observed Values, Repeated Measures Model) (PPS)

Table 14.2.3.4 Analysis of Change in Haemoglobin (g/dL) Over Time (Observed Values, Repeated Measures Model) (FAS)

Table 14.2.5.2 Analysis of Change in Transferrin Saturation (%) Over Time (Observed Values, Repeated Measures Model) (PPS)

Table 14.2.5.4 Analysis of Change in Transferrin Saturation (%) Over Time (Observed Values, Repeated Measures Model) (FAS)

Table 14.2.6.2 Analysis of Change in Serum Ferritin (ng/mL) Over Time (Observed Values, Repeated Measures Model) (PPS)

Table 14.2.6.4 Analysis of Change in Serum Ferritin (ng/mL) Over Time (Observed Values, Repeated Measures Model) (FAS)

Table 14.2.4.1 Summary of Subjects with Iron Deficiency Correction Over Time by Treatment (PPS)

Table 14.2.4.3 Summary of Subjects with Iron Deficiency Correction Over Time by Treatment (FAS)

Table 14.2.4.2 Analysis of Iron Deficiency Correction Over Time (Observed Values, logistic Model) (PPS)

Table 14.2.4.4 Analysis of Iron Deficiency Correction Over Time (Observed Values, Repeated Measures Model) (FAS)

Table 14.3.1.1 Overall Summary of Treatment Emergent Adverse Events

Table 14.3.1.2 Treatment Emergent Adverse Events by Primary System Organ Class and Preferred Term

Table 14.3.1.3 Treatment Emergent Treatment Related Adverse Events by Primary System Organ Class and Preferred Term

Table 14.3.1.4 Treatment Emergent Serious Adverse Events by Primary System Organ Class and Preferred Term

Table 14.3.1.5 Treatment Emergent Treatment Related Serious Adverse Events by Primary System Organ Class and Preferred Term

Table 14.3.1.6 Treatment Emergent Adverse Events Leading to Premature Study Withdrawal by Primary System Organ Class and Preferred Term

Table 14.3.1.7 Treatment Emergent Adverse Events Leading to Death by Primary System Organ Class and Preferred Term

Table 14.3.1.8 Treatment Emergent Adverse Events Leading to Study Drug Interruption by Primary System Organ Class and Preferred Term

Table 14.3.1.9 Treatment Emergent Adverse Events by Primary System Organ Class, Preferred Term, and Relationship to Study Medication

Table 14.3.1.10 Treatment Emergent Adverse Events by Primary System Organ Class, Preferred Term, and Maximum Severity

Table 14.3.1.11 Treatment Emergent Adverse Events by Preferred Term

Table 14.3.2.1.1 Summary of Laboratory Haematology Data (Absolute and Change from Baseline) Over Time

Table 14.3.2.2.1 Summary of Laboratory Biochemistry Data (Absolute and Change from Baseline) Over Time

Table 14.3.2.3 Summary of Laboratory Iron Parameters Data (Absolute and Change from Baseline) Over Time

Table 14.3.2.4.1 Summary of Laboratory Urinalysis Data (Absolute and Change from Baseline) Over Time

Table 14.3.2.1.2 Laboratory Data - Haematology Shift over Time by Treatment

Table 14.3.2.2.2 Laboratory Data - Biochemistry Shift over Time by Treatment

Table 14.3.2.1.3 Potentially Clinically Significant Post-Baseline Haematology Results

Table 14.3.2.2.3 Potentially Clinically Significant Post-Baseline Biochemistry Results

Table 14.3.2.4.2 Potentially Clinically Significant Post-Baseline Urinalysis Results

Table 14.3.3.1 Vital Signs Data (Absolute and Change from Baseline) Over Time

Table 14.3.4.1 12-Lead Electrocardiogram Data (Absolute and Change from Baseline) Over Time

Table 14.3.4.2 12-Lead ECG by Visit and Overall Interpretation

Table 14.3.4.3 Summary of Electrocardiogram Abnormal Results (QT and QTcF) by Treatment Group and Visit

Table 14.3.4.4 Electrocardiogram - QT and QTcF Shift Over Time by Treatment

Listing 16.2.1.1.1 Subjects Disposition (Safety)

Listing 16.2.1.1.2 Subjects Disposition (Screened Only/Not Treated)

Listing 16.2.1.2 Randomisation Assignments

Listing 16.2.2.1 Inclusion/Exclusion Criteria Description

Listing 16.2.2.2.1 Inclusion/Exclusion Criteria Failed (Safety)

Listing 16.2.2.2.2 Inclusion/Exclusion Criteria Failed (Screened Only/Not Treated)

Listing 16.2.3 Protocol Deviations

Listing 16.2.4 Subject Populations

Listing 16.2.5.1 Demographic and Baseline Characteristics (Safety)

Listing 16.2.5.2 Demographic and Baseline Characteristics (Screened Only/Not Treated)

Listing 16.2.6.1 Medical History (Safety)

Listing 16.2.6.2 Medical History (Screened Only/Not Treated)

Listing 16.2.7.1 Prior and Concomitant Medications (Safety)

Listing 16.2.7.2 Prior and Concomitant Medications (Screened Only/Not Treated)

Listing 16.2.8.1 Prior and Concomitant Procedures (Safety)

Listing 16.2.8.2 Prior and Concomitant Procedures (Screened Only/Not Treated)

Listing 16.2.9.1 Study Medication Exposure

Listing 16.2.9.2 Study Medication Compliance

Listing 16.2.10.1 Efficacy Haemoglobin (g/dL)

Listing 16.2.10.2 Efficacy Transferrin Saturation (%)

Listing 16.2.10.3 Efficacy Serum Ferritin (ng/mL)

Listing 16.2.10.4 Listing of Iron Deficiency Correction Data

Listing 16.2.11.1.1 Treatment Emergent Adverse Events

Listing 16.2.11.1.2 Non-Treatment Emergent Adverse Events

Listing 16.2.11.1.3 Adverse Events (Screened Only/Not Treated)

Listing 16.2.11.2 Treatment Emergent Treatment Related Adverse Events

Listing 16.2.11.3 Treatment Emergent Serious Adverse Events

Listing 16.2.11.4 Treatment Emergent Adverse Events Leading to Premature Study Withdrawal

Listing 16.2.11.5 Treatment Emergent Adverse Event Leading to Death

Listing 16.2.11.6 Special Situations

Listing 16.2.12.1 Laboratory Reference Ranges

Listing 16.2.12.2 Haematology Results

Listing 16.2.12.3 Biochemistry Results

Listing 16.2.12.4 Iron Parameters Results

Listing 16.2.12.5 Urinalysis Results

Listing 16.2.12.6 Hepatitis B and C Results

Listing 16.2.12.7 Serum Pregnancy Test

Listing 16.2.12.8 Subjects with Potentially Clinically Significant Assessment

Listing 16.2.12.9 Laboratory Data

Listing 16.2.13.1 Vital Signs (Safety)

Listing 16.2.13.2 Vital Signs (Screened Only/Not Treated)

Listing 16.2.14.1.1 12-Lead Electrocardiogram Results (Safety)

Listing 16.2.14.1.2 12-Lead Electrocardiogram Results (Screened Only/Not Treated)

Listing 16.2.14.2.1 Overall Interpretation of 12-Lead Electrocardiogram Results (Safety)

Listing 16.2.14.2.2 Overall Interpretation of 12-Lead Electrocardiogram Results (Screened Only/Not Treated)

Appendix 4: Laboratory assessments: CTC criteria (CTCAE V4.0)

Note: all laboratory PCS or CTC grading is provided for use in medical monitoring/on site monitoring and will not be used for reporting or severity classification of any adverse events/findings.

			CTC Grade				
Laboratory Sub Category	Laboratory Parameter	PCS Criteria	1	2	3	4	5
Haematology	Erythrocytes	Below LLN					
	Mean corpuscular volume	Below LLN>week 4					
	Mean corpuscular haemoglobin	Below LLN>week 4					

			CTC Grade				
Laboratory Sub Category	Laboratory Parameter	PCS Criteria	1	2	3	4	5
	Mean corpuscular haemoglobin concentration	Below LLN>week 4					
	Haemoglobin	Increase of two CTC grade or to grade 4	LLN-100.0 g/L LLN-6.2 mmol/L	<100.0-80.0 g/L <6.2-4.9 mmol/L	<80.0 – 65 g/L <4.9- mmol/L	Life-Threatening consequences, urgent intervention indicated	Death
	Haematocrit	Below LLN>week 4					
	Reticulocyte count	Below LLN>week 4					
	HbA1C	Below LLN>week 4					
	Leukocytes	Increase of two CTC grades or to grade 4	<LLN - 3.0 x 10 ⁹ /L	<3.0 - 2.0 x 10 ⁹ /L	<2.0 - 1.0 x 10 ⁹ /L	<1.0 x 10 ⁹ /L	Death
	Neutrophils	Increase of two CTC grades or to grade 4	<LLN - 1500/mm ³ ; <LLN - 1.5 x 10 ⁹ /L	<1500 - 1000/mm ³ ; <1.5 - 1.0 x 10 ⁹ /L	<1000 - 500/mm ³ ; <1.0 - 0.5 x 10 ⁹ /L	<500/mm ³ ; <0.5 x 10 ⁹ /L	
	Eosinophils	Below LLN					
	Basophils	Below LLN					
	Lymphocytes	Increase of two CTC grades or to grade 4	<LLN - 800/mm ³ ; <LLN - 0.8 x 10 ⁹ /L	<800 - 500/mm ³ ; <0.8 - 0.5 x 10 ⁹ /L	<500 - 200/mm ³ ; <0.5 - 0.2 x 10 ⁹ /L	<200/mm ³ ; <0.2 x 10 ⁹ /L	
	Lymphocytes	Above ULN		>4000/mm ³ - 20,000/mm ³	>20,000/mm ³		
	Monocytes	Below LLN					
	Platelets	Increase of two CTC grade or to grade 4	<LLN - 75.0 x 10 ⁹ /L	<75.0 – 50.0 x 10 ⁹ /L	<50.0 – 25.0 x 10 ⁹ /L	<25.0 x 10 ⁹ /L	Death
Serum Chemistry	Phosphorus - low	Grade 2 or above	<LLN - 2.5 mg/dL; <LLN - 0.8 mmol/L	<2.5 - 2.0 mg/dL; <0.8 - 0.6 mmol/L	<2.0 - 1.0 mg/dL; <0.6 - 0.3 mmol/L	<1.0 mg/dL; <0.3 mmol/L; lifethreatening consequences	Death
	Calcium (total, corrected and ionised) -	Grade 2 or above	Corrected serum calcium of >ULN -	Corrected serum calcium of >11.5 -	Corrected serum calcium of >12.5 - 13.5	Corrected serum calcium of >13.5	Death

			CTC Grade				
Laboratory Sub Category	Laboratory Parameter	PCS Criteria	1	2	3	4	5
	High		11.5 mg/dL; >ULN - 2.9 mmol/L; Ionised calcium >ULN - 1.5 mmol/L	12.5 mg/dL; >2.9 - 3.1 mmol/L; Ionised calcium >1.5 - 1.6 mmol/L; symptomatic	mg/dL; >3.1 - 3.4 mmol/L; Ionised calcium >1.6 - 1.8 mmol/L; hospitalisation indicated	mg/dL; >3.4 mmol/L; Ionised calcium >1.8 mmol/L; life-threatening consequences	
	Calcium (total, corrected and ionised) - low	Grade 2 or above	Corrected serum calcium of <LLN - 8.0 mg/dL; <LLN - 2.0 mmol/L; Ionised calcium <LLN - 1.0 mmol/L	Corrected serum calcium of <8.0 - 7.0 mg/dL; <2.0 - 1.75 mmol/L; Ionised calcium <1.0 - 0.9 mmol/L; symptomatic	Corrected serum calcium of <7.0 - 6.0 mg/dL; <1.75 - 1.5 mmol/L; Ionised calcium <0.9 - 0.8 mmol/L; hospitalisation indicated	Corrected serum calcium of <6.0 mg/dL; <1.5 mmol/L; Ionised calcium <0.8 mmol/L; life-threatening consequences	Death
	Glucose	Increase by two CTC grades or to grade 4	<LLN - 55 mg/dL; <LLN - 3.0 mmol/L	<55 - 40 mg/dL; <3.0 - 2.2 mmol/L	<40 - 30 mg/dL; <2.2 - 1.7 mmol/L	<30 mg/dL; <1.7 mmol/L; lifethreatening consequences; seizures	Death
	Hs C-reactive protein	Above ULN and greater than baseline result*					
	Sodium - high	Increase by two CTC grades or to grade 4	>ULN - 150 mmol/L	>150 - 155 mmol/L	>155 - 160 mmol/L	>160 mmol/L	Death
	Sodium - low	Increase by two CTC grades or to grade 4	<LLN - 130 mmol/L	-	<130 - 120 mmol/L	<120 mmol/L	Death
	Potassium - high	Increase by two CTC grades or to grade 4	>ULN - 5.5 mmol/L	>5.5 - 6.0 mmol/L	>6.0 - 7.0 mmol/L; hospitalisation indicated	>7.0 mmol/L; life-threatening consequences	Death
	Potassium - low	Increase by two CTC grades or to grade 4	<LLN - 3.0 mmol/L	<LLN - 3.0 mmol/L; symptomatic; intervention indicated	<3.0 - 2.5 mmol/L; hospitalisation indicated	<2.5 mmol/L; life-threatening consequences	Death
	Magnesium - High	Increase by two CTC grades or to	>ULN - 3.0	-	>3.0 - 8.0 mg/dL;	>8.0 mg/dL; >3.30	Death

			CTC Grade				
Laboratory Sub Category	Laboratory Parameter	PCS Criteria	1	2	3	4	5
		grade 4	mg/dL; >ULN - 1.23 mmol/L		>1.23 - 3.30 mmol/L	mmol/L;life-threatening consequences	
	Magnesium - low	Increase by two CTC grades or to grade 4	<LLN - 1.2 mg/dL; <LLN - 0.5 mmol/L	<1.2 - 0.9 mg/dL; <0.5 - 0.4 mmol/L	<0.9 - 0.7 mg/dL; <0.4 - 0.3mmol/L	<0.7 mg/dL; <0.3 mmol/L; lifethreatening consequences	Death
	Chloride	Below LLN or above ULN					
Liver Enzymes (Serum)	Alkaline phosphatase (ALP)	increase of two CTC grade or to grade 4	>ULN – 2.5 x ULN	>2.5 – 5.0 x ULN	>5.0 – 20.0 x ULN	>20.0 x ULN	-
	Aspartate transaminase (AST)	increase of two CTC grade or to grade 4	>ULN – 3.0 x ULN	>3.0 – 5.0 x ULN	>5.0 – 20.0 x ULN	>20.0 x ULN	-
	Alanine transaminase (ALT)	Increase of two CTC grade or to grade 4	>ULN – 3.0 x ULN	>3.0 – 5.0 x ULN	>5.0 – 20.0 x ULN	>20.0 x ULN	-
	Lactate dehydrogenase (LDH)	Above ULN					
	Gamma-glutamyl transpeptidase (GGT)	Increase of one CTC grade or to grade 4	>ULN – 2.5 x ULN	>2.5 – 5.0 x ULN	>5.0 – 20.0 x ULN	>20.0 x ULN	-
Iron Status Parameters	Serum Iron	n/a					
	Total Iron	n/a					
	UIBC	n/a					
	Ferritin	Above 800 ng/ml at consecutive visits					
	Transferrin	n/a					
	Transferrin saturation	n/a					
Urinalysis	Urobilinogen	n/a					
	Leucocytes	n/a					
	Protein	Positive					
	Glucose	Positive					
	Bilirubin	Positive					
	Nitrite	Positive					

			CTC Grade				
Laboratory Sub Category	Laboratory Parameter	PCS Criteria	1	2	3	4	5
	Ketone	Positive					
	Blood	Trace/positive					
	Phosphorus	n/a					

“**” Subjects are permitted to have a hsCRP above the ULN at baseline per protocol.

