7.6.1 Procedures for Overdose

If an inadvertent overdosing of a subject (e.g., by a calculation error of the required iron dose) is detected, this must be reported as an AE (see Section 10, Evaluation, Recording and Reporting of AEs and SAEs).

Post-baseline iron parameters will be assessed at each visit using the central laboratory. In the case of iron accumulation the Investigator at the site will initiate corrective measures according to local guidelines for treatment of iron overload, if necessary.

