10.2.5 Signs and Symptoms of the Disease Under Study

Signs or symptoms of IDA and the underlying disease (e.g., heavy uterine bleeding (HUB), CKD) should not be classed as AEs as long as they are within the normal day-to-day fluctuation of the disease. If a sign or symptom of the disease has unexpectedly worsened in severity or frequency or changed in nature at any time during the study, the symptoms and signs should be recorded as AEs, and clearly marked as worsening of the signs or symptoms in the CRF.

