10.2.6 Clinical Laboratory Evaluations

A change in the value of a safety laboratory investigation can represent an AE if the change is clinically significant and clinically relevant or if, during treatment with the

investigational product, a shift of a parameter is observed from a normal value to a pathological value, or a further worsening of an already pathological value. When evaluating such changes, the extent of deviation from the reference range, the duration until return to the reference range, either while continuing treatment or after the end of treatment with the investigational product, and the range of variation of the respective parameter within its reference range, must be taken into consideration.

If, at the end of the treatment phase, there are pathological laboratory values which were not present at baseline, further clinical or laboratory investigations should be performed until the values return to within reference range or until a plausible explanation (e.g., concomitant disease) is found for the pathological laboratory values.

The Investigator should decide, based on the above criteria and the clinical condition of a subject, whether a change in a laboratory parameter is clinically significant and clinically relevant and therefore represents an AE. If the Investigator considers such an AE as serious (e.g., medically significant event fulfilling criteria as per Section 10.1.5, Serious Adverse Event) it must be reported as an SAE.

Iron parameters such as serum iron, TSAT, UIBC, serum ferritin, serum transferrin, Hb, and reticulocytes are expected to be out of range after administration of IV iron products, and will therefore not be considered as AEs. They can be classed as clinically significant but are usually not clinically relevant and therefore are not reported as AEs.

If a laboratory abnormality meeting the above criteria is a sign of a disease or syndrome only the diagnosis should be recorded in the CRF.

If a laboratory abnormality meeting the above criteria is not a sign of a disease or syndrome, the abnormality itself should be recorded in the CRF, along with a descriptor indicating if the test result is above or below the normal range (e.g., “elevated potassium,” as opposed to “abnormal potassium”).

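### The SAP's haemoglobin flag has no numeric trigger below a baseline of 100 g/L, and its ferritin flag has no by-arm table, so the safety comparison lacks two counts

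*SAP*

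**What the plan says.** **Hb flag.** In SAP Appendix 4 the PCS criterion for haemoglobin is "Increase of two CTC grade or to grade 4". Grade 1 runs from the lower limit of normal (LLN) to 100 g/L, grade 2 is "<100.0-80.0 g/L", and grade 3 runs from below 80 to 65 g/L. Grade 4 is "Life-Threatening consequences, urgent intervention indicated", with no Hb value.

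**Ferritin flag.** The ferritin row of the same appendix gives "Above 800 ng/ml at consecutive visits".

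**Outputs.** SAP 4.7.2 says that subjects with PCS results will be summarised by treatment group. Appendix 3 lists "Table 14.3.2.1.3 Potentially Clinically Significant Post-Baseline Haematology Results" and matching PCS tables for biochemistry and urinalysis, but none for iron parameters. Listing 16.2.12.8 covers subjects with a PCS assessment and is not limited by laboratory category. A note at the top of Appendix 4 says that PCS and CTC grading is for monitoring and is not for reporting or severity classification of adverse events or findings.

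**Adverse events.** Protocol 10.2.6 lists iron parameters and continues: "Hb, and reticulocytes are expected to be out of range after administration of IV iron products, and will therefore not be considered as AEs". Protocol 10.2.4 names IDA among the pre-existing conditions that become an AE if they worsen. Protocol 10.2.5 requires an AE entry "If a sign or symptom of the disease has unexpectedly worsened in severity or frequency".

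**The concern.** Comparing the safety of FCM and IS, and their effect on haematology and iron parameters, is a secondary objective. Inclusion criterion 2 admits only subjects with Hb below 11 g/dL (women) or 12 g/dL (men). A deterioration flag therefore has to work in people who already have a CTC grade at baseline. If it cannot fire for those starting below 10 g/dL, the Hb row of Table 14.3.2.1.3 will look reassuring in both arms whatever happens to them.

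The shift tables do not fill the gap. They use low, normal and high, so a subject who starts low and falls further stays low. The other red-cell flags are simply below LLN (for most of them, only after Week 4), which says little in a population selected for MCV, MCH and MCHC below fixed limits.

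For iron, Protocol 8.1 advises monitoring to avoid overload, and Protocol 7.6.1 says "In the case of iron accumulation the Investigator at the site will initiate corrective measures". The two arms can also plan different total iron for the same patient. A count by arm of subjects meeting the SAP's own ferritin rule is the natural summary, and no table delivers it.

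**Working it through.** The plan states no figure to reproduce here. The check applies the Appendix 4 bands to baseline and post-baseline Hb. Units: 10 g/dL = 100 g/L (SAP Appendix 2, factor 0.1). The LLN is not given, so 110, 115, 120 and 130 g/L were each tried.

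**Step 1: what can trigger the Hb flag from the value alone**

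| Baseline Hb (g/L) | Baseline grade | Grade needed | Numeric trigger |
|---|---|---|---|
| At or above LLN | 0 | 2 | below 100 |
| 100 to below LLN | 1 | 3 | below 80 |
| 80 to below 100 | 2 | 4 | none |
| 65 to below 80 | 3 | 4 | none |
| Below 65 | no numeric grade | 4 | none |

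Every whole-number baseline from 60 to 119 g/L was run against every lower value down to 40 g/L. No baseline below 100 g/L could be flagged, at any of the four LLNs.

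- 99 to 65 g/L: fall of 34 g/L = 3.4 g/dL, grade 2 to 3, one grade, not flagged.
- 100 to 79 g/L: fall of 21 g/L = 2.1 g/dL, grade 1 to 3, two grades, flagged.

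A value below the 6 g/dL (60 g/L) discontinuation limit in Protocol 7.6 also has no numeric grade, so it does not trigger the flag by number.

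**Step 2: is this peculiar to Hb?** Yes. Every other Appendix 4 row with a to-grade-4 rule (leukocytes, neutrophils, lymphocytes, platelets, glucose, sodium, potassium, magnesium and the graded liver enzymes) has a number at grade 4. Hb alone does not.

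**Step 3: ferritin.** PCS tables in Appendix 3: haematology, biochemistry, urinalysis. PCS tables for iron parameters: 0. PCS listings able to carry the ferritin flag: 1.

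**Step 4: why a by-arm ferritin count is worth having.** Ganzoni deficit = weight × (15 − Hb) × 2.4 + 500, rounded to the nearest 200 mg (Protocol 7.2.2), set against the FCM totals in Protocol Table 2 and its footnote:

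| Subject | Deficit (mg) | Rounded IS (mg) | FCM (mg) | FCM vs IS |
|---|---|---|---|---|
| 36 kg, Hb 9.9 | 36 × 5.1 × 2.4 + 500 = 941 | 1,000 | 1,500 | +50% |
| 70 kg, Hb 9.9 | 70 × 5.1 × 2.4 + 500 = 1,357 | 1,400 | 2,000 | +43% |
| 69 kg, Hb 10.0 | 69 × 5.0 × 2.4 + 500 = 1,328 | 1,400 | 1,000 | −29% |

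These are boundary cases. They show that exposure can differ by arm in either direction. They do not bear on which dose is right.

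**Step 5: what a numeric grade 4 would do.** If any Hb below 65 g/L counted as grade 4, all baselines from 65 to 99 g/L would become flaggable, at 64 g/L. From 99 g/L that is a fall of 3.5 g/dL; from 75 g/L it is 1.1 g/dL.

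**The case against.** A reader might infer that worsening anaemia or iron overload could go unseen. The documents do not support that.

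- Absolute Hb and ferritin and their changes are summarised by arm and visit with quartiles, minimum and maximum (SAP 4.1.1; Tables 14.2.3.x, 14.2.6.x, 14.3.2.1.1, 14.3.2.3). Both are compared by MMRM and listed per subject.
- Hb below 6 g/dL forces discontinuation (Protocol 7.6), and failing to act on it is a major deviation (SAP Appendix 1). Transfusion or ESA use forces withdrawal with the reason recorded.
- The PCS listing exists, and listings are ordered by treatment.

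A reader might also infer that nobody below 10 g/dL can ever be flagged. A clinician could assign the descriptive grade 4, so the limit is only that the laboratory value cannot do it.

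Nor is worsening anaemia barred from AE reporting. Protocol 10.2.6 exempts laboratory values and says they are usually not clinically relevant, while 10.2.4 and 10.2.5 still allow worsening disease to be recorded. What stands is that the sections pull different ways on a falling Hb, and sites could read them differently.

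On tables, Protocol 11.8 accepts clinically significant values being tabulated, listed, or both, so a listing alone would satisfy the protocol. It does not satisfy SAP 4.7.2, which promises a summary by treatment group; on that view the ferritin gap is one title missing from Appendix 3.

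The Appendix 4 note could be read as making the flags a monitoring aid only. Yet section 4.7.2 and Appendix 3 schedule PCS summaries, and a flag without a number cannot be computed for monitoring either.

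**Conclusion.** The point holds as a gap in safety reporting. For subjects with baseline Hb below 100 g/L, the Hb PCS flag cannot be derived from laboratory data, so Table 14.3.2.1.3 cannot count their deterioration by arm. The ferritin rule has no by-arm table despite SAP 4.7.2. The primary analysis, analysis sets and data collection are untouched.

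The documents do not give the share of subjects below 10 g/dL. If it were 50% to 90% (an assumption), the Hb flag would lack a numeric trigger for 368 × 0.5 = 184 to 368 × 0.9 = 331 subjects. That is the number the rule does not reach, and it should not be read as a number of missed deteriorations. The remark about the shift tables assumes that the LLN is at or above the entry limits. No ferritin distribution is given, so whether the arms would differ above 800 ng/mL is unknown.

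**What to change.** 1. **Appendix 4, Hb row.** Give a criterion computable from the laboratory value. One option is to treat any Hb below 65 g/L, the lower limit of the SAP's own grade 3, as grade 4 for flagging. Another, alone or in addition, is a pre-stated fall from baseline whose size the sponsor chooses. If only the first is used, say how subjects already below 65 g/L at baseline are handled; a fall-from-baseline rule covers them.
2. **Appendix 3.** Add a by-arm PCS table for iron parameters using the existing ferritin rule.
3. **Wording.** Reconcile the Appendix 4 note with section 4.7.2 and the planned PCS tables. Reconcile Protocol 10.2.6 with 10.2.4 and 10.2.5 on whether a falling Hb can be an AE.

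The cost is a little programming, one more table, and clarifying text in the SAP and protocol. No new data are needed.
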